### 14.3.7 Displays of 12-Lead Standard Electrocardiograms

**Table 38: Summary of Post Dose Electrocardiograms Change in Overall Interpretations from Baseline by Treatment Group and Time Point, Safety Population**

Change from Baseline in ECG Interpretation	400 mg SLV213 (N=X)		Placebo (N=X)		All Participants (N=X)	
	n	%	n	%	n	%
Day 4						
Normal at Both Times	x	xx	x	xx	x	xx
Normal to Abnormal, NCS						
Normal to Abnormal, CS						
Day 8						
Normal at Both Times	x	xx	x	xx	x	xx
Normal to Abnormal, NCS						
Normal to Abnormal, CS						
Note: N = Number of participants in the Safety Population with ECG measurements; n = Number of participants with the change from baseline interpretations.						
NCS = Not clinically significant; CS = Clinically significant.						

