- **Vital Signs (VS) inclusive of orthostatic blood pressure and heart rate:** Include body temperature (oral), BP (resting more than 5 min), RR, and HR. Heart rate and BP will be measured at rest with the participant supine for at least 5 minutes. VS will be measured twice daily within 30 min before and 2h (\pm 10 min) after each dose on Days 1 to 7, once daily in the morning on Days 8 and 9, or at ET. Abnormal VS may also be measured at unscheduled visits as needed for follow up of AEs. Repeat measurements with the participant supine may be allowed if the first measurement is abnormal (See [Section 8.3.3](#)).¹

Note 1: Orthostatic blood pressure and heart rate will be obtained and recorded after the supine VS, while the participant is in the standing position with measurements taken at 1 minute \pm 15 seconds and 3 minutes \pm 15 seconds after standing.

- **ECG:** A standard 12-lead ECG will be recorded, within 30 min before the morning dose on Day 4, on Day 8 before the 12h blood (plasma) PK collection after the evening dose on Day 7, or ET. Additional ECGs may be recorded as needed for the evaluation of TEAEs. The participant should be in a supine position and should have an approximate 10-minute rest period prior to ECG recordings.

A physician (PI or coinvestigator) or clinician who is licensed to make diagnoses (listed on Form FDA 1572) will evaluate the ECG for any abnormalities in ECG intervals including QT/QTcF, and any morphologic abnormalities for clinical significance. If a question regarding ECG interpretation arises, the study investigators will have the ECG reviewed by a cardiologist.

8.3.2 **Laboratory Evaluations**

- **Clinical Laboratory Assessments:**

- Blood for HEM, CHEM, and COAG will be collected before the morning dose on Days 2, 4, and 6, and on Day 8, or ET for the evaluation of the same tests listed in [Section 8.1.2](#). Clinical lab tests may also be performed at unscheduled visits as needed for follow up of AEs. Participants must be fasting at least for 4 h before any blood draw for clinical laboratory assessments.
- UA will be collected before the morning dose on Day 4 and on Day 8, or ET (See [Section 8.1.2](#))

8.3.3 **Procedures to be Followed in the Event of Abnormal Clinical Laboratory Test Values or Abnormal Clinical Findings During Conduct of the Trial**

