## 6. GENERAL STATISTICAL CONSIDERATIONS

### 6.1. General Principles

All continuous variables will be summarized using the following descriptive statistics: n (non-missing sample size), mean, standard deviation, median, maximum, and minimum. The frequency and percentages (based on analysis population sample size, unless otherwise stated) of observed levels will be reported for all categorical measures. In general, all data will be listed, sorted by treatment group, participant, parameter, and time point as applicable.

The Safety Population will be the primary population used for summaries of safety endpoints. The PK Analysis Population will be used for summaries of PK endpoints. Analyses of primary and secondary endpoints will be done for each dose of SLV213 and compared with a placebo group.

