#### Interim Safety Analyses

Interim safety analysis is not planned. Safety data may be summarized for *ad hoc* review as requested by the SMC. Top level safety parameters will be assessed between cohorts as needed.

After one participant experienced a moderate allergic reaction, further dosing was discontinued in four participants. As a result, four replacement participants were added at the advice of the SMC. One of these replacement participants also had a moderate allergic reaction to the study product. After meeting a halting rule criterion, the study was halted, and the SMC reviewed data of the two participants who reported a moderate allergic reaction. Under the advisement of the SMC, the study will not proceed with Cohort 2 and Cohort 3.

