## 9.9. Other Safety Measures

### 9.9.1. 12-Lead Standard Electrocardiogram

Unscheduled ECG measurements will be included in listings but will be excluded from tabular and graphical summaries by time point, except when calculating the maximum severity post baseline. Baseline is defined in [Section 3.1](#). Individual interval measurements and overall interpretations will be presented in [Listing 19](#) and [Listing 20](#), respectively.

---

The sort order for ECG interval measurements will be as follows: PR Interval, QRS Interval, QT Interval, QTcF Interval, RR Interval, and Ventricular Rate.

12-lead standard ECG results will be summarized in tables and figures:

- Summary of 12-lead standard ECG change in overall interpretation from baseline will be shown by treatment group and time point (**Table 38**).
- Number and percentage of participants with mild, moderate, severe, or life-threatening ECG results by parameter, time point, and treatment group (**Table 39**).

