**Table 39: ECG Results by Parameter, Severity, Treatment Group, and Time Point, Safety Population (continued)**

Time Point	Treatment Group	N	None		Mild/ Grade 1		Moderate/ Grade 2		Severe/ Grade 3		Life-Threatening/ Grade 4	
			n	%	n	%	n	%	n	%	n	%
Day 8	400 mg SLV213											
	...											
Max Severity Post Baseline	400 mg SLV213											
	...											
QTcF Interval												
Day -1 (Baseline)	400 mg SLV213		X	X	XX	X	XX	X	XX	X	XX	X
	...											
Day 4	400 mg SLV213											
	...											
Day 8	400 mg SLV213											
	...											
Max Severity Post Baseline	400 mg SLV213											
	...											

Note: The “Max Post Baseline” rows indicate the maximum severity experienced by each participant at any time point post baseline, including unscheduled assessments.  
N = Number of participants in the Safety Population with the laboratory result assessed at the respective time point; n = Number of participants with the maximum grade experienced for the specified parameter and time point.

[figure not shown]

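### SAP Table 38 puts one column N over both the Day 4 and Day 8 ECG shifts, and has no any-time row for overall interpretation

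*SAP*

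**What the plan says.** Table 38 (SAP Appendix 1, 14.3.7) summarises the change in overall ECG interpretation from baseline. Each treatment column carries a single N in its header, above a Day 4 block and a Day 8 block. Each block has three rows: normal at both times, normal to abnormal not clinically significant (NCS), and normal to abnormal clinically significant (CS). The note reads "N = Number of participants in the Safety Population with ECG measurements". The table has no row for missing ECGs, for participants abnormal at baseline, or for any time after baseline.

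Table 39, the next ECG display, has an N for each time point, defined as "N = Number of participants in the Safety Population with the laboratory result assessed at the respective time point". The laboratory wording is carried over, but N is tied to the visit. Tables 33 and 37 define N in the same way. Table 39 also has maximum-severity rows, which "rows indicate the maximum severity experienced by each participant at any time point post baseline, including unscheduled assessments". Its parameters are PR and QTcF, plus a row for any ECG parameter.

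SAP 9.9.1 says: "Unscheduled ECG measurements will be included in listings but will be excluded from tabular and graphical summaries by time point". The same sentence makes an exception for maximum post-baseline severity. SAP 6.1 sets the default base: "The frequency and percentages (based on analysis population sample size, unless otherwise stated) of observed levels will be reported for all categorical measures".

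Post-dose ECGs are scheduled for Day 4 and Day 8, or at early termination (Protocol 1.2 and 8.3.1). In addition, "Additional ECGs may be recorded as needed for the evaluation of TEAEs". SAP 6.2 reports what happened in Cohort 1: "After one participant experienced a moderate allergic reaction, further dosing was discontinued in four participants". Four replacements were then added, and SAP 6.3.3 keeps everyone who was dosed, replacements included, in the Safety Population.

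**The concern.** A by-visit percentage should rest on the people measured at that visit. Table 38 departs from the convention of the SAP's other by-visit safety tables, in a cohort where early stopping makes missed visits plausible. The arms are so small that one or two absent ECGs move a percentage by several points. If the arms lose different numbers, the comparison of SLV213 with placebo shifts as well.

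The second issue is coverage. Table 38 is the only planned summary of overall interpretation, which can include morphology that no interval grade reflects. An ECG taken at early termination or to evaluate an event is among the more informative ones, yet its overall interpretation has no row there.

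**Working it through.** **The plan's own figure.** There is none to reproduce, because Table 38 is an empty shell.

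**Inputs.**
- Planned Cohort 1: 8 SLV213 and 4 placebo (SAP 2.1, 4.1 and 5). SAP Table 4 prints 6 for the 400 mg group; the text figure of 8 is used here.
- Stopped: 4. Replacements: 4 (SAP 6.2). The Safety Population could reach 8 + 4 + 4 = 16.
- Not given: the arms of the stopped participants, and whether each had a Day 4 or Day 8 ECG.

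**Assumption.** In a given arm, k stopped participants have some ECG that counts towards N but none on the day shown. Their replacements receive the same treatment (Protocol 7.2.2), and everyone else has the ECG. Then N = planned arm size + k, and n_t = planned arm size.

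**Formulas.** For x shifts, Table 38 prints 100·x/N. The day-based figure is 100·x/n_t. Their ratio is n_t/N. With x = 1:

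| Arm | k | N | n_t | Table 38 | Day-based | n_t/N |
|---|---|---|---|---|---|---|
| SLV213 | 0 | 8 | 8 | 12.5% | 12.5% | 1.00 |
| SLV213 | 2 | 10 | 8 | 10.0% | 12.5% | 0.80 |
| SLV213 | 4 | 12 | 8 | 8.3% | 12.5% | 0.67 |
| Placebo | 0 | 4 | 4 | 25.0% | 25.0% | 1.00 |
| Placebo | 2 | 6 | 4 | 16.7% | 25.0% | 0.67 |
| Placebo | 4 | 8 | 4 | 12.5% | 25.0% | 0.50 |
| All | 4 | 16 | 12 | 6.25% | 8.3% | 0.75 |

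**Who is in N.** If any ECG qualifies, the Day -1 ECG puts everyone dosed into N. If only post-dose ECGs qualify, a stopped participant still enters N through an early-termination ECG: Protocol 7.1.3 refers to the Early Termination column for data at discontinuation of study drug, and that column includes an ECG. On neither reading does N depend on the day.

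**Where an abnormal overall interpretation from an early-termination or unscheduled ECG can appear.**
- Table 38: no row.
- Table 39, maximum-severity rows: only as a graded PR or QTcF finding.
- Table 14: only if Grade 3.
- Tables 22 to 25: only if reported as an adverse event.
- Listing 20: always, but as an individual line.

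**The case against.** The strongest reply is that little is lost. A reader might infer that early-termination and event-driven ECGs are tabulated nowhere. The documents do not support that. SAP 9.9.1 lets unscheduled ECGs into maximum post-baseline severity, Table 39 has rows for it, and Table 14 counts Grade 3 ECG findings at any post-dose time. Tables 22 and 23 include ECG adverse events, Protocol 8.3.3 treats abnormal post-treatment findings as adverse events, and Listing 20 links clinically significant readings to an adverse event number. This stands. The gap is confined to the overall interpretation, and its main content is ungraded readings judged not clinically significant.

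A reader might also infer that a participant without that day's ECG is counted as unchanged. That is not so. Unchanged participants have their own row, and a participant without an ECG enters no row. All three percentages shrink by one factor, so the balance of shift to no shift within an arm is preserved and the counts remain correct. This stands too. But with neither a missing row nor an abnormal-at-baseline row, the day's true denominator cannot be recovered from the printed counts.

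The dilution itself is conditional. Protocol 7.1.3 and 7.2.1 keep participants who stop drug in the study, so no ECG need be missing. The halving on placebo requires all four stops to be on placebo. That sits badly with SAP 4.1, which says the 400 mg group met the halting rules, so it is only an outer limit.

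Finally, a fixed N follows the SAP 6.1 default, and the note is loosely worded rather than plainly wrong. That is fair, but Tables 33, 37 and 39 all depart from the default for by-visit results. Nothing explains why Table 38 should not.

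**Conclusion.** The point holds as a modest defect in one shell. Table 38 is out of line with Tables 33, 37 and 39 in its denominator, and it lacks the any-time row that Table 39 has.

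The effect ranges from none, if every scheduled ECG was done, to a factor of 8/12 = 0.67 on SLV213 if all four stopped participants were in that arm and lacked the ECG. One shift would then print as 8% instead of 13%. This rests on the arm size of 8 in the SAP text and on the assumption that everyone else had the ECG. The documents give neither the arms of the stopped participants nor the number of missing ECGs. The study is descriptive, so no test or decision rule is affected. The consequence is a percentage that may be too low, and an interpretation summary that omits early-termination and unscheduled readings.

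**What to change.** In Table 38, replace the header N with n/N at each time point, where N is the number of Safety Population participants with both a baseline ECG and an ECG at that time point. Add a third block for the worst overall interpretation at any time after baseline, including early-termination and unscheduled ECGs, with its own N. Amend the note to match, and extend the exception in SAP 9.9.1 so that it covers worst overall interpretation as well as maximum severity.

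The cost is a change to the shell, one sentence of SAP text and the programming. The data are already collected for Listing 20. SAP section 15 allows an addendum before final data lock, so the change should be made by then.

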**Table 39: ECG Results by Parameter, Severity, Treatment Group, and Time Point, Safety Population**

[Implementation Note: ECGs will be presented for Days -1 (baseline), 4, and 8 for each treatment group.

If there are no life-threatening/grade 4 vital signs reported, then the columns will be omitted. If there is not at least one graded event for a treatment group within a parameter, then only “Max Severity Post Baseline” will be shown. If there are more than one graded event within a parameter for a specified time point, then report the maximum severity.

Parameters will be shown in the following order: Any ECG Parameter, PR Interval, and QTcF Interval.]

Time Point	Treatment Group	N	None		Mild/ Grade 1		Moderate/ Grade 2		Severe/ Grade 3		Life-Threatening/ Grade 4	
			n	%	n	%	n	%	n	%	n	%
Any ECG Parameter												
Day -1 (Baseline)	400 mg SLV213		x	x	xx	x	xx	x	xx	x	xx	x
	Placebo											
	All Participants											
Day 4	400 mg SLV213											
	...											
Day 8	400 mg SLV213											
	...											
Max Severity Post Baseline	400 mg SLV213											
	...											
PR Interval												
Day -1 (Baseline)	400 mg SLV213		x	x	xx	x	xx	x	xx	x	xx	x
	Placebo											
	All Participants											
Day 4	400 mg SLV213											
	...											

**Table 39: ECG Results by Parameter, Severity, Treatment Group, and Time Point, Safety Population (continued)**

Time Point	Treatment Group	N	None		Mild/ Grade 1		Moderate/ Grade 2		Severe/ Grade 3		Life-Threatening/ Grade 4	
			n	%	n	%	n	%	n	%	n	%
Day 8	400 mg SLV213											
	...											
Max Severity Post Baseline	400 mg SLV213											
	...											
QTcF Interval												
Day -1 (Baseline)	400 mg SLV213		X	X	XX	X	XX	X	XX	X	XX	X
	...											
Day 4	400 mg SLV213											
	...											
Day 8	400 mg SLV213											
	...											
Max Severity Post Baseline	400 mg SLV213											
	...											

Note: The “Max Post Baseline” rows indicate the maximum severity experienced by each participant at any time point post baseline, including unscheduled assessments.  
N = Number of participants in the Safety Population with the laboratory result assessed at the respective time point; n = Number of participants with the maximum grade experienced for the specified parameter and time point.

[figure not shown]

### 9.5.1 Safety Measurements Assessed and Flow Chart

**Figure 1: Schematic of Study Design**

[figure not shown]
[Implementation Note: Pulled from Protocol v4.0 Section 1.3.]

## 10.1 Disposition of Participants

**Figure 2: CONSORT Flow Diagram**

**[Implementation Note:** Treatment groups will be 400 mg SLV213 and Placebo. “Reasons for Exclusion” and the associated footnote will only be listed if at least one participant was excluded from the specified population for the specified reason in the given treatment group. ‘x’ will be replaced with the number of participants that meet the criteria. If any participants received the incorrect dose at any point in time, a footnote will be attached to “Completed all dosesa” of the given treatment group and the following footnote will be added: “a X participants received at least one incorrect dose.” The asterisks will be updated to footnote (b), if applicable. A footnote will be added before footnotes (a) and (b): “Note: The study was terminated prior to enrollment to Cohorts 2 (600 mg SLV213) and 3 (800 mg SLV213).”]

[figure not shown]

\*Note: a participant may meet multiple exclusion criteria.

## 14.2.2 Pharmacokinetics

### Figure 3: Individual SLV213 Concentration in Plasma Profiles – Day 1, Morning Dose

[Implementation Note: The figure will consist of individual concentrations at each nominal time point: t=0 (pre-dose), 1h, 2h, 4h, 6h, 8h, and 12h. The y-axis will be labeled “Concentration in Plasma (ng/mL)” with the maximum concentration as the max and the minimum concentration as the min. The x-axis will be labeled “Time (h)” with tick marks at each nominal time point. Data points should represent actual time of collection.]

### Figures with similar format:

### Figure 4: Individual SLV213 Concentration in Plasma Profiles – Day 7, Evening Dose

[figure not shown]
[Implementation Note: Dose 14 nominal time points are t=0 (pre-dose), 1h, 2h, 4h, 6h, 8h, 12h, 24h, 36h, and 48h.]

### Figure 5: Individual Trough SLV213 Concentration in Plasma Profiles – Day 1 to Day 7, All Doses

[Implementation Note: Trough concentrations are defined as concentrations collected 12 hours after each morning and evening dose. Note, 12 hours post dose will also be considered as t=0 (pre-dose) for the proceeding dose. The x-axis label will be “Doses” with a tick mark for each dose number.]

**Figure 6: Semi-Log Individual SLV213 Concentration in Plasma Profiles – Day 1, Morning Dose**

[Implementation Note: The figure will consist of individual concentrations at each nominal time point: t=0 (pre-dose), 1h, 2h, 4h, 6h, 8h, and 12h. The y-axis will be in the log-10 scale and labeled “Concentration in Plasma (ng/mL)” with the maximum concentration as the max and the minimum concentration as the min. The x-axis will be labeled “Time (h)” with tick marks at each nominal time point. Data points should represent actual time of collection.]

**Figures with similar format:****Figure 7: Semi-Log Individual SLV213 Concentration in Plasma Profiles – Day 7, Evening Dose**

[Implementation Note: Dose 14 nominal time points are t=0 (pre-dose), 1h, 2h, 4h, 6h, 8h, 12h, 24h, 36h, and 48h.]

[figure not shown]
**Figure 8: Semi-Log Trough SLV213 Concentration in Plasma Profiles – Day 1 to Day 7, All Doses**

[Implementation Note: Trough concentrations are defined as concentrations collected 12 hours after each morning and evening dose. Note, 12 hours post dose will also be considered as t=0 (pre-dose) for the proceeding dose. The x-axis label will be “Doses” with a tick mark for each dose number.]

#### 14.3.1.2 Unsolicited Adverse Events

[figure not shown]
**Figure 9: Frequency of Related Adverse Events by MedDRA System Organ Class and Severity**

[Implementation Note: This figure will include serious and non-serious unsolicited adverse events deemed related to the study product. It will be paneled by treatment group: 400 mg SLV213 and Placebo. The SOCs will be sorted by descending frequency with “Any SOC” at the top.]

**Figure 10: Incidence of Related Adverse Events by MedDRA System Organ Class and Maximum Severity**

[Implementation Note: This figure will include serious and non-serious unsolicited adverse events deemed related to the study product. It will be paneled by treatment group: 400 mg SLV213 and Placebo. The SOCs will be sorted by descending incidence with “Any SOC” at the top.]

**Listing 1: 16.1.6: Listing of Participants Receiving Investigational Product**

[Implementation Note: Listing will be sorted by Treatment Group, Participant ID, Date, and Time.]

Treatment Group	Participant ID	Study Day (Dose)	Date	Time
		Day 1 (Morning)	ddMMMyyyy	hh:mm

## 16.2 Database Listings by Participant

### 16.2.1 Discontinued Participant

#### Listing 2: 16.2.1: Early Terminations or Discontinued Participants

[Implementation Note: Listing will be sorted by Treatment Group, Participant ID, Category, and Study Day.]

Treatment Group	Participant ID	Category	Reason for Early Termination or Treatment Discontinuation	Study Day

## 16.2.2 Protocol Deviations

### Listing 3: 16.2.2.1: Participant-Specific Protocol Deviations

[Implementation Note: Listing will be sorted by Treatment Group, Participant ID, and DV Number.]

Treatment Group	Participant ID	DV Number	Deviation	Deviation Category	Study Day	Reason for Deviation	Deviation Resulted in AE?	Deviation Resulted in Participant Termination?	Deviation Affected Product Stability?	Deviation Classification	Deviation Resolution	Comments

**Listing 4: 16.2.2.2: Non-Participant-Specific Protocol Deviations**

[Implementation Note: Listing will be sorted by Site, Start Date, and Deviation.]

DV Number	Deviation	Deviation Category	Start Date	End Date	Reason for Deviation	Deviation Resulted in Participant Termination?	Deviation Affected Product Stability?	Deviation Classification	Deviation Resolution	Comments

### 16.2.3 Participants Excluded from the Safety and/or PK Analysis

#### Listing 5: 16.2.3: Participants Excluded from Analysis Populations

**[Implementation Note:** This listing should be congruent with “Analysis Populations by Treatment Group” ([Table 11](#)). Only participants who were excluded from at least one analysis population will be included in this listing. Participants who were excluded from multiple analysis populations will have a separate line per analysis population excluded from in the listing.]

Listing will be sorted by Treatment Group, Participant ID, Analyses Included, and Analyses Excluded.]

Treatment Group	Participant ID	Analyses in which Participant is Included	Analyses from which Participant is Excluded	Results Available?	Reason Participant Excluded
		[e.g., Full Analysis, Safety, mITT, PK]	[e.g., Safety, mITT, PK (All Visits)]		Safety: Did not receive study product mITT, PK: Excluded from Safety Population

Note: “Yes” in the “Results available” column indicates that available data were removed from the analysis. “No” indicates that no data were available for inclusion in the analysis.

